The primary objective of this study is to evaluate the efficacy of nebulized heparin administration in COVID-19. Our primary outcome will be defined as the mean PaO₂/FiO₂ ratio in the first 10 days of ICU stay. This is the gold standard for hypoxia monitoring in ARDS. Our secondary safety outcome will include clinically significant bleeding, defined as transfusion of red blood cells, required intervention for new-onset bleeding, or death attributed to bleeding during the study period. Additional outcomes will include incidence of VTE, time on mechanical ventilation, ICU duration, and overall mortality.

Study Design: Describe the study design (e.g., single/double blind, parallel, crossover, etc.). Indicate whether or not the subjects will receive placebo medication at some point in the research procedures. Also, indicate whether or not the subjects will be randomized in this study. You may reference sponsor's protocol pages and attach as an appendix in the E-IRB "Additional Information" section, however, a summary paragraph must be provided in the text box below. (Including the study design table from a sponsor's protocol is helpful to IRB members.)

Community-Based Participatory Research: If you are conducting community-based participatory research (CBPR), describe strategies for involvement of community members in the design and implementation of the study, and dissemination of results from the study.

Research Repositories: If the purpose of this submission is to establish a Research Repository (bank, registry) indicate whether the material you plan to collect would or would not be available from a commercial supplier, clinical lab, or established IRB approved research repository. Provide scientific justification for establishment of an additional repository collecting duplicate material. Describe the repository design and operating procedures. For relevant information to include, see the UK Research Biospecimen Bank Guidance [PDF] or the UK Research Registry Guidance [PDF]

We propose a randomized, controlled pilot study of patients admitted with confirmed COVID-19 receiving mechanical ventilation for ARDS (paO₂/FiO₂ ratio =300) within 48 hours. Enrollment will occur by the ICU research team who perform daily review for study enrollment. Patients will be randomized to nebulized heparin (25,000 units in 3 mL sodium chloride [NaCl] every 6 hours) versus

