placebo (5 mL nebulized NaCl every 6 hours) for 10 days or until successful ventilator wean. Drugs will be dispensed by investigational drug services. Patients will be excluded for a history of heparin allergy, terminal status as determined by attending physician, history of thrombosis (prior VTE or cardiovascular event), high risk of bleeding (platelet count < 50,000/ μ L or international normalized ratio > 1.5), or active bleeding. Monitoring will include daily ventilator parameters, complete metabolic panels, and complete blood counts, as well as hourly vital signs as part of standard care. The MICU also has an actively enrolling biobank with respiratory samples which we will use to assess viral load. Additional samples will be collected for coagulation (protein S, thrombin, and histone) monitoring, at baseline, 72 hours, and day 10. Laboratory results, medication administration, and vital sign data will be collected up until 10 days of ICU admission or discharge. Mortality, length of stay, and mechanical ventilation duration will be collected for the entire hospital stay. Based on expected baseline $\text{paO}_2/\text{FiO}_2$ ratio of 118 mmHg, we calculate that we need a sample size of 46 patients (n=23 per group) to detect a 15% improvement in $\text{paO}_2/\text{FiO}_2$ ratio, assuming an alpha of 0.05 and power of 80%. (22)

Attachments

[Back to Top](#)

Study Population: Describe the characteristics of the subject population, such as anticipated number, age range, gender, ethnic background and health status. Identify the criteria for inclusion and exclusion. Explain the rationale for the use of special classes such as fetuses, pregnant women, children, institutionalized, adults with impaired consent capacity, prisoners, economically or educationally disadvantaged persons or others who are likely to be vulnerable.

If women or minorities are included, please address how the inclusion of women and members of minority groups and their subpopulations will help you meet your scientific objectives. Exclusion of women or minorities requires clear and compelling rationale that shows inclusion is inappropriate with respect to the health of the subjects or that inclusion is inappropriate for the purpose of the study. Cost is not an acceptable reason for exclusion except when the study would duplicate data from other sources. Women of childbearing potential should not be excluded routinely from participation in clinical research.

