The following will be recorded from standard of care documentation: demographics (age, sex, race, past medical history), chief complaint, past medical history, blood gases, medications, and transfusions administered and dosing, mechanical ventilation parameters, complete blood counts, complete metabolic panels, and vital signs. Patient outcomes including in-hospital mortality, Murray Lung Injury Score, ICU and hospital length of stay, the incidence of venous thromboembolism, the incidence of pulmonary embolism, the incidence of clinically significant bleeding, and duration of mechanical ventilation. Lab values for coagulation (protein S, thrombin, and histone) monitoring with an additional blood draw at baseline, 72 hours, and day 10.

Attachments

Resources: Describe what resources/facilities are available to perform the research (i.e., staff, space, equipment). Such resources may include a) staffing and personnel, in terms of availability, number, expertise, and experience; b) psychological, social, or medical services, including counseling or social support services that may be required because of research participation; c) psychological, social, or medical monitoring, ancillary care, equipment needed to protect subjects; d) resources for subject communication, such as language translation services, and e) computer or other technological resources, mobile or otherwise, required or created during the conduct of the research. Please note: Some mobile apps may be considered mobile medical devices under FDA regulations (see [FDA Guidance](#)). Proximity or availability of other resources should also be taken into consideration, for example, the proximity of an emergency facility for care of subject injury, or availability of psychological support after participation.

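### The primary outcome window runs from ICU admission rather than from randomisation, so untreated days are averaged in, late treated days can be lost, and the effect is diluted

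*Protocol*

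**What the plan says.** **Outcome.** The Objectives section of the protocol states: "Our primary outcome will be defined as the mean" PaO2/FiO2 "ratio in the first 10 days of ICU stay". The clock is the ICU stay. Randomisation and first dose are not mentioned in the definition.

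**Data window.** The Study Design section collects laboratory results, medication and vital-sign data until day 10 of the ICU admission or until discharge. Only mortality, length of stay and ventilation duration are followed for the whole hospital stay. The Data Collection section lists "blood gases, medications, and transfusions administered and dosing, mechanical ventilation parameters" among the items taken from routine charting.

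**Path to randomisation.** Study Design requires mechanical ventilation for ARDS, with a 48-hour limit, and finds patients at a daily review. The Research Procedures and Informed Consent Process sections place screening and consent, often from a representative reached by telephone, before randomisation. Treatment then runs for 10 days or until successful weaning.

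**Sizing.** "Based on expected baseline" PaO2/FiO2 "ratio of 118 mmHg, we calculate that we need a sample size of 46 patients (n=23 per group", chosen "to detect a 15% improvement in" the ratio, "assuming an alpha of 0.05 and power of 80" per cent. No SD is given.

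**The concern.** Two clocks are in use. The outcome and the data collection count from ICU admission; the treatment counts from randomisation. They agree only for a patient randomised at the moment of ICU admission, and the steps required before randomisation make that unlikely to be typical.

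For everyone else two things follow:

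- Ratios recorded before allocation are averaged into the primary outcome. They cannot be affected by treatment, so they pull the arm means together.
- For a patient treated for the full 10 days, a delay of k days pushes the last k treated days outside both the outcome and the data collection.

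Both weaken the contrast in a trial of 46 patients with no stated dropout allowance. The definition sits in the protocol itself, so a statistical analysis plan that implements it faithfully would inherit the problem.

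**Working it through.** **Inputs**

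- From Study Design: reference ratio 118 mmHg, improvement 15%, 23 per arm, alpha 0.05, power 80%.
- Not in the document, so assumed: a two-sided test; the 15% read as a between-arm difference; the outcome SD; the delay from ICU admission to first treatment.

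**Step 1: the plan's own figure.** The target is 0.15 × 118 = 17.7 mmHg. Without an SD, the 23 per arm can be neither confirmed nor refuted. Solving backwards gives the SD it needs:

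- Normal approximation: SD = 17.7 / [(1.960 + 0.842) × √(2/23)] = 21.4 mmHg.
- t distribution: 21.0 mmHg.

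I use 21 mmHg, so the starting point is the plan's own 80%.

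**Step 2: dilution.** If k of the 10 outcome days come before treatment and the effect is constant afterwards, the expected between-arm difference in the 10-day mean is 17.7 × (10 − k)/10. The standard error is 21 × √(2/23) = 6.19 mmHg. Power is from the noncentral t with 44 degrees of freedom and noncentrality equal to difference / 6.19. The SD of the 10-day mean is held unchanged.

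| Untreated days k | Expected difference (mmHg) | Noncentrality | Power |
|---|---|---|---|
| 0 | 17.7 | 2.86 | 80% |
| 1 | 15.9 | 2.57 | 71% |
| 2 | 14.2 | 2.29 | 61% |
| 3 | 12.4 | 2.00 | 50% |

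**Step 3: what does not depend on the SD.** The required sample size scales with 1/(1 − k/10)². To keep the planned power, 23 per arm becomes 23/0.81 = 28.4, 23/0.64 = 35.9 or 23/0.49 = 46.9, that is 29, 36 or 47 per arm for 1, 2 or 3 untreated days. This factor holds for any SD, provided the effect is constant and the SD is the same in both windows.

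**Step 4: sensitivity to the SD.** At an assumed SD of 40 mmHg the same calculation (standard error 40 × √(2/23) = 11.8) gives 31% power with no delay and 26%, 22% and 18% with 1, 2 and 3 untreated days. The relative loss remains, but the missing SD would then be the larger problem.

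**Step 5: the baseline ratio as a covariate.** With the window moved, the last ratio before randomisation is a clean covariate. The residual SD is SD × √(1 − r²), with 43 degrees of freedom. At SD 21 and r = 0.3, 0.5 and 0.7, power goes from 80% to about 83%, 90% and 97%. At SD 40 it goes from 31% to about 34%, 40% and 54%. The document gives no value for r.

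**The case against.** **The wording may be loose.** The outcome sentence may mean the first 10 study days, and a unit that screens daily may randomise many patients on their first ICU day, in which case the loss is small. This is fair as to size, since the delay is unknown. It does not rescue the text, because Study Design repeats the ICU-admission clock for data collection.

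**The damage is dilution, not bias against one arm.** This stands. Randomisation makes the untreated days comparable between arms on average.

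**A reader might infer more than the protocol supports:**

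- *That each patient's baseline ratio goes unused and the comparison is unadjusted.* No analysis model is stated; Research Procedures says only that de-identified data go to the statistician. A 10-day mean is a perfectly good outcome for a covariate-adjusted model, and covariates are commonly left to the analysis plan, which is not at hand. Silence is not a choice of an unadjusted test.
- *That outcome and sizing describe different quantities.* The 15% can be read as change from a patient's own baseline, but it fits equally well as 17.7 mmHg between arms with 118 as the reference level, and then the two agree. The comparator is unstated, not contradictory.
- *That a chance imbalance in starting ratio passes straight into the result.* With equal SDs only about r times the imbalance carries over. An imbalance of half the target, 17.7/2 = 8.85 mmHg, shifts the result by about 2.7 mmHg at r = 0.3 and 4.4 mmHg at r = 0.5. The unadjusted estimate stays unbiased, and its standard error already allows for chance imbalance.
- *That adjustment is free.* It costs one degree of freedom, and the gain depends on a correlation that nobody has stated.

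**Conclusion.** The point holds as a defect in the outcome window. The primary outcome and its data collection are tied to ICU admission while allocation and treatment start later, so the text as written averages in untreated values and can drop late treated ones.

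Under the stated assumptions each untreated day removes a tenth of the expected difference, and one to three such days bring power from 80% to between 71% and 50%. These figures rest on an SD inferred from the sample size, a two-sided between-arm reading of the 15%, a constant effect from randomisation and an assumed delay. An effect that builds up slowly would lose more, because the days cut off are the late ones; an early, short-lived effect would lose less from that truncation. Patients weaned before day 10 of the ICU stay lose no treated days, though their untreated days still count.

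The document does not show that the baseline ratio is ignored or that the planned analysis is wrong. Baseline adjustment is a recommendation only.

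**What to change.** In the Objectives section, define the primary outcome as the mean PaO2/FiO2 over the 10 days after randomisation, with values before randomisation excluded from the average. In Study Design, count the laboratory, medication and vital-sign collection window from randomisation as well. In the sizing sentence, state that the 15% (17.7 mmHg) is the between-arm difference in that mean, and give the SD used.

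Recommended in addition: name the last ratio before randomisation as a covariate in a linear model with treatment arm (ANCOVA). The ratio is an entry criterion, and blood gases and ventilator settings are already recorded, so the value should exist for every patient.

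The cost is a few sentences, one degree of freedom if the covariate is used, and a short extension of data collection for patients randomised after their first ICU day. The treatment schedule is not affected. The change should be made before any comparison by arm. For patients whose collection has already stopped at ICU day 10, the missing later days would need to be retrieved from the chart.

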Once subjects are identified per the above process, an assessment will be made as described in form T by the study team member of whether the patient can provide informed consent. If ineligible, a legally authorized representative will be approached regarding the study. Informed consent will be sought once the patient meets the eligibility criteria as defined in the study protocol. If the legally authorized representative is not physically in the hospital due to visiting restrictions due to COVID-19, an electronic consent process will be sought as follows. The patient's LAR will be contacted via telephone and approached about the study in the same way that the LAR would be if they were physically present. If the LAR is interested in pursuing further, a member of the study team will send the LAR a RedCap link that has been designed for e-consent in this study. A member of the study team will walk the LAR through the e-consent document, which mirrors the written informed consent document exactly, and answer any questions along the way. If the LAR consents, they will sign the document using the e-sign feature in RedCap. A member of the study team will email the LAR back with a copy of the signed e-consent form.

[Back to Top](#)

Research Procedures: Describe the research procedures that will be followed. Identify all procedures that will be carried out with each group of subjects. Differentiate between procedures that involve standard/routine clinical care and those that will be performed specifically for this research project.

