Patients will be screened for eligibility by a member of the research team. If a patient meets eligibility, then a team member will approach the LAR for informed consent. After enrollment, the patient will be randomized via an online randomization generator to either nebulized heparin (25,000 units in 3 mL sodium chloride [NaCl] every 6 hours) or placebo (5 mL nebulized NaCl every 6 hours) for 10 days or until successful ventilator wean. The nurse will be approached for a 10 mL blood draw to be performed at baseline, 72 hours, and day 10 to assess protein S, thrombin, and histone in the [name] laboratory (BBSRB B306-15 and B306-16). The study team will collect the blood samples. Up to 10 mL of blood will be drawn each time for a maximum of 30 mL total, collected in citrate-containing tubes. Deidentified data will be collected via RedCap from the standard of care charting. Upon study completion, deidentified data will be sent to the statistician for analysis.

Attachments

Data Collection: List the data or attach a list of the data to be collected about or from each subject (e.g. interview script, survey tool, data collection form for existing data).

If the research includes survey or interview procedures, the questionnaire, interview questions or assessment scales should be included in the application (use attachment button below).

The data collection instrument(s) can be submitted with your application in draft form with the understanding that the final copy will be submitted to the IRB for approval prior to use (submit final version to the IRB for review as a modification request if initial IRB approval

was issued while the data collection instrument was in draft form).

Note: The IRB approval process does not include a statistical review. Investigators are strongly encouraged to develop data management and analysis plans in consult with a statistician.

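### The primary P/F mean is counted from ICU admission, but study drug starts only after randomisation, and the two 10-day clocks are never aligned

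*Protocol*

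**What the plan says.** All references are to the protocol's Research Description.

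- **Outcome window.** Objectives: the primary outcome is the mean PaO2/FiO2 "ratio in the first 10 days of ICU stay".
- **Data window.** Study Design uses the same origin: "Laboratory results, medication administration, and vital sign data will be collected up until 10 days of ICU admission or discharge".
- **Treatment window.** Study Design and Research Procedures: drug or placebo is given "for 10 days or until successful ventilator wean".
- **Start of treatment.** Informed Consent Process: "Informed consent will be sought once the patient meets the eligibility criteria as defined in the study protocol". Research Procedures: "After enrollment, the patient will be randomized via an online randomization generator to either nebulized heparin" or placebo.
- **Sample size.** Study Design: "we need a sample size of 46 patients (n=23 per group) to detect a 15% improvement in" the P/F ratio, from an expected baseline of 118 mmHg, with alpha 0.05 and 80% power. The improvement is not tied to a time window.
- **Other timings.** Blood samples are taken "at baseline, 72 hours, and day 10". Data Collection lists "blood gases, medications, and transfusions administered and dosing, mechanical ventilation parameters" with no cut-off day.
- **48-hour limit.** Study Design attaches a 48-hour limit to ventilation for ARDS without saying what it is counted from. The inclusion sentence under Study Population does not carry it.

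**The concern.** The outcome and the treatment each last 10 days but start at different events. The outcome starts at ICU admission. Treatment starts after daily screening, an eligibility check, consent (possibly by telephone and electronic signature from an absent representative), enrolment and randomisation. Any gap puts untreated days at the front of the primary mean and can push treated days off its end.

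P/F is the only outcome for which the trial is sized, with 23 patients per group. A weaker contrast in that mean directly reduces the chance of seeing an effect that is really there.

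**Working it through.** **1. The two clocks side by side.** Take k = 2, with the first treated day on ICU day 3 and a full 10-day course.

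- Outcome: ICU days 1 to 10.
- Treatment: ICU days 3 to 12.
- Untreated days in the outcome: ICU days 1 and 2.
- Treated days outside the outcome: ICU days 11 and 12.

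Late P/F values may still be recorded, since Data Collection sets no cut-off, but they are not part of the outcome as defined. A patient weaned or discharged before ICU day 10 loses no late treated days, but the early untreated days then form a larger share of a shorter series.

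**2. Is k bounded?** Not clearly. The 48-hour limit names no starting event. If it runs from the start of ventilation, a patient ventilated some days into the ICU stay still brings earlier days into the window. On the most favourable reading, 48 hours from ICU admission, k can still reach 2.

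**3. The plan's own figure.** The inputs are baseline 118 mmHg, 15% improvement, n = 23 per group, alpha 0.05 and power 80%. The effect is 0.15 × 118 = 17.7 mmHg. No SD is stated, so 46 cannot be reproduced forwards and the SD has to be back-solved. For a two-sample t-test with n = 23 per group, 80% two-sided power needs a standardised difference of d = 0.845, so SD = 17.7 / 0.845 = 21.0 mmHg (21.4 by the normal approximation). One-sided, d = 0.745 and SD = 23.8 mmHg.

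**4. Dilution if 17.7 mmHg is the effect on each treated day.** Let w be the share of a patient's P/F days in the window that precede treatment. Assume no effect on those days, a constant effect afterwards, the same w for everyone and an unchanged SD. The effect in the primary mean is then 17.7 × (1 − w). Power comes from the noncentral t distribution.

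| w | Example | Effect in the mean (mmHg) | Power, two-sided | Power, one-sided |
|---|---|---|---|---|
| 0 | k = 0, or no blood gas before treatment | 17.7 | 80% | 80% |
| 10% | k = 1 of 10 P/F days | 15.9 | 71% | 72% |
| 20% | k = 2 of 10 | 14.2 | 61% | 63.5% |
| 33% | k = 2 of 6 (early wean or discharge) | 11.8 | 46% | 50.5% |

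An average lag of half a day in ten (w = 5%) gives 16.8 mmHg and 76% two-sided. Restoring 80% two-sided would take about 29 per group at w = 10% and 36 at w = 20%.

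**5. If 17.7 mmHg is already the difference in the ICU-day mean.** The 80% stands, but the effect per treated day must be 17.7 / (1 − w):

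- w = 10%: 17.7 / 0.9 = 19.7 mmHg, or 16.7% of 118
- w = 20%: 17.7 / 0.8 = 22.1 mmHg, or 18.8%
- w = 33%: 17.7 / (2/3) = 26.55 mmHg, or 22.5%

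**The case against.** The strongest reply has four parts.

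- **The sample size refers to the outcome as defined.** The only P/F outcome in the protocol is the ICU-day mean, so 15% is most naturally the difference in that mean, and no power is lost. This is fair, and step 5 covers it. The cost then appears as a larger effect demanded of the drug on treated days, which the protocol does not acknowledge.
- **The lag may be small.** The 48-hour limit can be read as an enrolment limit, screening is daily, and early ICU days may have no blood gas. All of this reduces w, and a trial-wide w of 33% is unlikely because it applies an early-wean case to every patient. But eligibility itself requires ventilation and a P/F value, so at least one pre-randomisation value is expected, and it falls inside the window if measured in the ICU. The limit also does not cover patients first ventilated later in their ICU stay.
- **Randomisation balances pre-treatment days.** It does, on average. That rules out systematic bias but not dilution.
- **This is a pilot, and details belong in the SAP.** The pilot label lowers the stakes. But the protocol itself fixes the origin of the window, so an analysis plan that follows it inherits the mismatch.

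If study days were intended all along, the text is wrong as written and needs the same edit.

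**Conclusion.** The concern holds. The mismatch is plain from the text: the outcome and its data window count from ICU admission, treatment counts from after randomisation, and nothing aligns them. This should be fixed.

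The size of the harm cannot be pinned down, because the protocol gives no SD, lag distribution or sidedness. For a pre-treatment share of 10% to 20%, the cost is either a fall in two-sided power from 80% to between 71% and 61%, or a rise in the required effect per treated day from 15% to between 16.7% and 18.8%, depending on what the 15% refers to. The power figures rest on a back-solved SD of 21.0 mmHg, a constant effect on treated days and the same share for every patient. The harm is nil for patients randomised on the day of ICU admission. Late treated days are lost only for patients still on drug after ICU day 10.

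**What to change.** 1. In Objectives, define the primary outcome as the mean P/F over the 10 days from randomisation. Keep pre-randomisation values out of the outcome; they remain available as baseline.
2. In Study Design, change the window for laboratory, medication and vital-sign data to 10 days after randomisation or discharge.
3. Separately, reconcile Study Design and Study Population on the 48-hour limit, and state the event it is counted from.

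The cost is a few wording changes, plus a few more days of routine chart data for patients randomised after ICU admission. No extra patients or procedures are needed.

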intensive care unit and subject to the intensive monitoring required from the baseline care of such a population. Once the database has been completed from information collected, identifiable information will be removed and replaced with a subject ID number. The PI will maintain a logbook of the ID number with patient identifiers in a locked cabinet in a locked office. If clinically significant bleeding occurs during drug treatment, defined as transfusion of red blood cells thought to be secondary to investigational drug or required intervention for new-onset bleeding secondary to investigational drug, the drug will be automatically stopped.

Benefit vs. Risk: Describe potential benefits to the subject(s); include potential benefits to society and/or general knowledge to be gained. Describe why the risks to subjects are reasonable in relation to the anticipated benefit(s) to subjects and in relation to the importance of the knowledge that may reasonably be expected to result. If you are using vulnerable subjects (e.g., impaired consent capacity, pregnant women, etc...), justify their inclusion by describing the potential benefits of the research in comparison to the subjects' vulnerability and the risks to them. For information about inclusion of certain vulnerable populations, see the IRB/ORI Standard Operating Procedure for Protection of Vulnerable Subjects [C3.0100] [\[PDF\]](#).

We do not know if subjects in this group will benefit directly, but hypothesized benefits of the use of nebulized heparin include decreased length of stay and decreased lung injury scores. Risks are outlined in the informed consent document and notably include the risk of bleeding. Given the mortality rate in patients with ARDS secondary to COVID-19, there may be patients that benefit from this drug despite the minimal risks. We have attempted to use the literature to guide our protocol to reflect those patients most likely to benefit.

Available Alternative Treatment(s): Describe alternative treatments and procedures that might be advantageous to the subjects, should they choose not to participate in the study. This should include a discussion of the current standard of care treatment(s).

There are no alternative treatments. Patients enrolled will continue to receive standard of care therapies per the discretion of the primary team. Thromboprophylaxis is permitted per standard of care. Patients who require systemic anticoagulation will be excluded from this study.

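### The transfusion limb of the bleeding outcome is not tied to bleeding, and the same name carries a second, narrower definition elsewhere in the protocol

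*Protocol*

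**What the plan says.** The Objectives section introduces the safety outcome with "Our secondary safety outcome will include clinically significant bleeding" and defines it as "clinically significant bleeding, defined as transfusion of red blood cells, required intervention for new-onset bleeding, or death attributed to bleeding during the study period". No other safety outcome is named there.

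The Safety Precautions section uses the same term for an event during drug treatment that stops the study drug. It has its own definition: "defined as transfusion of red blood cells thought to be secondary to investigational drug or required intervention for new-onset bleeding secondary to investigational drug".

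The Data Collection section lists "transfusions administered and dosing" among the charted items. Separately, among patient outcomes, it lists "the incidence of clinically significant bleeding". It gives no definition for the second item and refers to neither of the other two sections. No indication for transfusion is listed. The source is routine charting (Research Procedures): "Deidentified data will be collected via RedCap from the standard of care charting".

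**The concern.** A reader who applies the Objectives definition literally must count every patient who received red cells, whatever the reason. The protocol attaches bleeding risk to this drug, and its Potential Risks section calls such events rare. When true bleeds are few, a handful of unrelated transfusions can make up much of the count. The reported rate would then partly describe transfusion practice.

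The second definition adds to the uncertainty. A transfusion not thought to be due to the drug is an event under the Objectives wording and not under the Safety Precautions wording, yet both carry one name. Whoever fills in the bleeding item on the data form is not told which definition to use.

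What is at stake is the meaning of the descriptive bleeding rates that this pilot will report. The primary outcome and the sample size are not affected.

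**Working it through.** **Step 1: set the definitions side by side.**

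| Element | Objectives (outcome) | Safety Precautions (trigger) |
|---|---|---|
| Red-cell transfusion | Any; no link to bleeding or to drug | Only if attributed to study drug; bleeding not named |
| Intervention | For new bleeding | For new bleeding, attributed to study drug |
| Death | If attributed to bleeding | Not listed |
| Timing | Study period | During drug treatment |

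In the Objectives column, the transfusion row is the only one without a bleeding condition. The trigger's transfusion row cannot be read back to repair it, because it ties transfusion to the drug and not to bleeding.

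**Step 2: check whether the listed data settle the matter.** Data Collection lists transfusions without an indication, and bleeding incidence without a definition. The listed items alone do not ensure that non-bleeding transfusions are kept out of the bleeding count.

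**Step 3: the size that the document supports.** The protocol states no expected bleeding rate and no power for this outcome, so there is no stated figure to reproduce. Study Design gives n = 23 per group. One patient counted only because of a non-bleeding transfusion adds

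1/23 = 0.0435, or 4.3 percentage points, to that arm's rate.

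**Step 4: illustration only, on an assumed rate.** Let p be the true bleeding risk and t the risk of a non-bleeding transfusion. Assume that t is equal in both arms and independent of bleeding. The document gives no value for t; the range below is an assumption.

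- Counted risk = 1 − (1 − p)(1 − t), so the inflation is t(1 − p).
- Counted risk difference = (1 − t)(p₁ − p₀), for any p₁ and p₀.
- In an arm with no bleeding (p = 0), expected counted events = 23t, and the chance of at least one is 1 − (1 − t)²³.

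| Assumed t | Expected counted events, p = 0 | Chance of at least one | Factor on risk difference |
|---|---|---|---|
| 5% | 1.15 | 69% | 0.95 |
| 10% | 2.30 | 91% | 0.90 |
| 20% | 4.60 | 99% | 0.80 |
| 40% | 9.20 | over 99.9% | 0.60 |

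The table shows the direction and form of the effect. It does not estimate what this trial will see.

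**The case against.** **The intent is clear enough.** The term being defined is a kind of bleeding, so the three limbs can be read as criteria that make a bleed clinically significant. Data Collection also records bleeding as its own item, so it need not be derived from the transfusion log. This is probably what was meant. But the other two limbs repeat the bleeding condition, the transfusion limb omits it, and the data list does not supply it. The written rule still miscounts.

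**A literal reading may be a defensible choice.** All-cause transfusion is objective, needs no adjudication and captures occult bleeding. That advantage is real. It is kept if all-cause transfusion is reported under its own name beside the bleeding outcome.

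**The two definitions may serve two purposes.** A safety outcome and a drug-stop trigger can properly differ, and as written every trigger event also meets the outcome definition. No patient is directed to incompatible actions. A reader might infer that the protocol contradicts itself on when to stop the drug; the text does not support that, since the narrower trigger may be deliberate. What stands is that one name carries two definitions and the data item does not say which it follows.

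**The time window.** A reader might also infer a fault from Study Design, which sets one window in "Laboratory results, medication administration, and vital sign data will be collected up until 10 days of ICU admission or discharge" and another in "Mortality, length of stay, and mechanical ventilation duration will be collected for the entire hospital stay" without naming transfusion or bleeding in either. That is unstated detail which a data form or analysis plan could supply. It is not an error in the text, and it forms no part of this point.

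**The outcome is minor.** It is secondary and descriptive in a 46-patient pilot, the Objectives wording leaves room for other safety outcomes, and the Data and Safety Monitoring section has investigators review all adverse events. This stands, and it limits the weight of the point.

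**Conclusion.** The point holds as a minor correction. The transfusion limb in Objectives lacks the bleeding condition that the other two limbs have, so the stated rule counts non-bleeding transfusions as bleeds and inflates the reported rates. The same name is defined differently in Safety Precautions, and Data Collection does not choose between the two. An analysis plan that is not shown could add adjudication detail, but the protocol would still hold two definitions under one name.

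The only size that rests on the document is 4.3 points per misclassified patient at 23 per arm. The total is unknown. A reader might infer from the illustrative table that the comparison between arms will be badly diluted, or that the power to detect harm is lost. The documents support neither: they give no transfusion rate, and the outcome was never powered. Nor can the 5% and 2% rates from the cited ARDS trial in Background stand in for bleeding rates, since they are described there as adverse events. No changed trial decision is claimed.

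**What to change.** - In Objectives, word the first limb as red-cell transfusion given for bleeding, regardless of suspected cause.
- Report all-cause red-cell transfusion by arm alongside the composite, from the transfusion data already listed in Data Collection.
- In Data Collection, point the bleeding item to the Objectives definition.
- Reconcile Objectives with Safety Precautions, for example by using separate names for the outcome and the stopping trigger. The content of the stopping rule is left to the investigators.

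The cost is a phrase, a cross-reference, a change of name and one extra descriptive line in the results. There is a small downside: deciding why a transfusion was given needs judgement from the chart, and the protocol describes no masked outcome assessment, so that judgement is best made without knowledge of arm. Occult bleeding transfused as anaemia would appear only in the all-cause count, which is a further reason to report both.
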